Urine samples will be collected at every visit, and we will use onsite testing to provide immediate feedback on opiate use to the participant and the treatment team. Blood chemistry will be obtained at baseline and end of study (week 25). Urine Pregnancy tests will be obtained at baseline, at once monthly (or prior to administration of XR-NTX).

We will collect 4ml of saliva, 50ml of urine, and 4, 6-7ml blood from subjects at Baseline, after randomization (3 weeks after 1st injection of XR-NTX, or 1 week after completing bup taper), during post randomization month 2 (1 week after 2nd XR-NTX injection, or 4 weeks after completion of bup taper), and at end of study to be examined for biomarkers. From these we will isolate extracellular vesicle-containing pellets and evaluate their contents using advanced -OMICs analyses, in order to identify molecular signatures that differ across subjects before and after ending treatment with buprenorphine.

Assessment Instruments

Create a table or give a brief description of the instruments that will be used for assessment

Physiological Measures

Medical History and Physical Exam: A comprehensive medical history and physical examination will be performed during the screening process. All potential participants will be offered the opportunity to be referred to receive free HIV risk reduction education, as well as HIV testing and counseling.

Pregnancy Testing: Serum pregnancy testing will be performed on all females during screening and urine pregnancy tests will be performed at baseline and monthly afterwards.

Serum laboratory examination: Complete blood count, electrolyte, and liver function tests will be performed during the screening process and at the end of study.

Urinalysis: Laboratory urinalysis (glucose, protein, ketones, pH, specific gravity, and microscopic analysis) will be performed during the screening process and at the end of study.

Urine Toxicology: Urine samples will be collected under directly--observed conditions during screening and at each study visit. To provide immediate feedback to the participant, the Abuscreen On--Trak system (Roche Diagnostics) will be used to identify opiates (morphine, oxycodone, buprenorphine, methadone). In addition, the sample will be analyzed for substances of abuse, including THC, alcohol, opioids, cocaine, benzodiazepines, amphetamines, and barbiturates.

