Systematic Assessment for Treatment and Emergent Events (SAFTEE): The SAFTEE as modified for Project COMBINE (Johnson et al., 2005) will be performed weekly, **and twice-monthly during study months 4-6** to identify any adverse symptoms. If participants report experiencing adverse symptoms since the previous visit, the research nurse will record the symptom as well as the date of onset, severity, and resolution (if applicable) and research psychiatrist will review it at least weekly and more frequently if symptoms are present.

Timeline Follow--Back (TLFB): The Timeline Followback method (Litten and Allen, 1992) will gather self-- reported opioid use data for each day during the month prior to study enrollment and each day during the study period. The TLFB confirmed by urine toxicology will be the primary outcome measure of psychoactive substance use and will be performed at **every study visit**.

Therapist Contact Log (TCL): The number and duration of treatment sessions will be documented by the therapist on a contact log.

End of Study Form (ESF): At study completion or the point of termination for patients who relapse or drop out, the research psychiatrist fills out an End of Study Form, which indicates whether or not a patient completed 25 weeks of treatment, the date of termination, the number of weeks of treatment completed from randomization to termination, and reasons for early termination, including documented relapse to opiates, resumption of buprenorphine maintenance, psychiatric worsening, medical worsening, or lost to follow--up.

Self--Report

Clinical Global Impression--Self (CGI--S): The CGI--Self is a two--item scale that asks the subject to rate his or her current level of symptoms and estimate changes from baseline (Guy, 1976). The CGI--S will serve as the primary self--reported measure of overall functioning.

Medical Outcomes Study--Sleep Scale (MOS--SS): The MOS--SM is a 12--item measure for characterizing the quality of sleep (Hays et al., 2005). Opioid withdrawal, both acute and protracted is characterized by insomnia and other sleep disturbances. The MOS--SM will be the primary outcome of sleep quality and length and will be collected at each visit.

Craving Scales-- Self: A visual analog scales is used for patients to rate the intensity of craving for opiates experienced since the previous visit ([name] et al., 2011).

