study visits vitals and a urine toxicology for opioids (morphine, oxycodone, buprenorphine, methadone, propoxyphene, and fentanyl), THC, cocaine, benzodiazepines, amphetamines, and metamphetamines will be collected. They will have scheduled meetings with a study psychiatrist weekly to inquire about medication effects and any changes in their medical/psychological condition following medication discontinuation.

The primary outcome will be the percent of patients successfully transitioned off buprenorphine and abstinent from any opioids at the 25-week trial endpoint. Secondary outcomes will include measures of opioid withdrawal, mood, anxiety and sleep problems, abstinence from other substances, time to relapse or dropout, and adverse effects. We hypothesize that more patients will successfully discontinue buprenorphine in the group that received XR-NTX.

This proposed exploratory trial will be able to inform the design of future research and clinical work. A positive signal that transition from maintenance buprenorphine to XR-NTX is feasible and prevents relapse would encourage a larger trial to replicate and perhaps extend to multiple community based treatment settings. A feasible, well-tolerated, and effective method of helping patients wishing to discontinue treatment with BUP has the potential to expand the population of opioid-dependent individuals benefitting from treatment.

A2. Primary and Secondary Outcome Measures

Primary Outcome: percent of patients successfully transitioned off buprenorphine and abstinent from any opioids at the 25-week trial endpoint.

Secondary Outcomes: 1) Measures of weekly opiate withdrawal (SOWS), mood (Ham-D, BDI), anxiety (HAM-A, STAI), and sleep (MOS-SS) (continuous, longitudinal); 2) Time to relapse (survival outcome); 3) Continuing abstinence at 12 and 25 weeks (dichotomous); 4) Dichotomous weekly summary measure of use (derived by combining urine and self-report, as measured by TLFB) reflecting whether each patient had urine-confirmed opiate-free weeks over the course of treatment and urine-confirmed abstinence from all drugs (dichotomous, longitudinal); 5) Adverse events (SAFTEE) (dichotomous).

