Covariates/Predictor variables: 1) Length of BUP treatment prior to randomization and the average dose; 2) Demographic characteristics (e.g., gender, age); 3) Baseline presence of co-occurring mood or anxiety disorders; 4) Baseline severity of opioid use (measured by the primary opioid, route, and quantity of illicit opioid use per using day prior to starting BUP treatment); 5) Duration of OUD, 6) Other substance use during treatment period.

A3. Inclusion/Exclusion Criteria

The following inclusion/exclusion criteria will be used for selection of participants in the proposed study.

Inclusion Criteria	Method of Ascertainment
1. Individuals between the ages of 18-60	ID with birth date
2. A documented history of treatment with buprenorphine or buprenorphine/naloxone for at least 6 months with sustained abstinence from illicit opioids for at least 3 months. Participants must be maintained on daily dose of buprenorphine in the 2-8 mg range.	MINI interview by therapist, Clinical interview by psychiatrist, consultation with previous prescriber or the verification patient's self-report with the prescribing records (PMP) with patient's permission

3. In otherwise good health based on complete medical history, physical examination, vital signs measurement, ECG, and laboratory tests (hematology, blood chemistry, urinalysis) within normal ranges	Medical history and physical examination by psychiatrist or NP, laboratory tests (serum Chem-20 and CBC, urinalysis), ECG
4. Seeking buprenorphine discontinuation and willing to accept randomization to either taper from buprenorphine or injection naltrexone	Clinical interview by psychiatrist
5. Able to give written informed consent to participate in the study	Clinical Interview by psychiatrist

Exclusion Criteria	Method of Ascertainment
1. Lifetime history of DSM-5 diagnosis of schizophrenia, schizoaffective disorder, or bipolar disorder	MINI interview by therapist, Clinical interview by psychiatrist
2. Current DSM-5 criteria for any other psychiatric disorder that in the investigator's judgment is unstable, would be disrupted by the study medication, or is likely to require pharmacotherapy or psychotherapy during the study period. Concurrent treatment with other psychotropic medication that is stable for the last 3 months is not exclusionary.	MINI interview by therapist, Clinical interview and mental status exam by psychiatrist, contact with collateral information as needed and available

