Study Aim #2: To determine whether treatment with XR-NTX reduces severity of protracted withdrawal seen following BUP discontinuation.

Significance testing and preliminary analysis:

All tests for main effects will be performed at two-tailed significance $\alpha=5\%$. We will examine all variables for outliers, the distributions of all continuous variables will be checked for normality and if needed transformations will be used before applying parametric techniques. The distribution of demographic variables and other covariate measures at baseline in the treatment arms will be examined (means, standard deviations, proportions and 95% confidence intervals). The analysis will be adjusted by three preselected covariates (primary opioid type, length of BUP maintenance, and average dose).

Primary Analyses

Subjects treated with XR-NTX will have significantly higher rates of successful transition off BUP at the end of study compared to subjects tapered off BUP. The effect of treatment on the primary outcome will be examined using logistic regression adjusted for specified covariates (primary opioid type, length of BUP maintenance, and average dose), and described using the estimated coefficients of the treatment term in the model, the corresponding odds ratios, and 95% confidence intervals.

Secondary Analyses

Longitudinal dichotomous and continuous outcomes will be modeled with generalized linear mixed effects models using appropriate link function (logit for dichotomous outcomes) with treatment, time, treatment by time interaction, and applicable baseline outcome measure as predictors. Time to relapse will be analyzed using survival analyses and Kaplan-Meier estimators. Dichotomous outcomes will be analyzed similarly to primary hypothesis with logistic regressions. The within subject correlation will be modeled using autoregressive AR(1) structure and random effects of subject. Significant time by treatment interaction indicates different change over time between treatment groups. If the interaction between time and treatment is not found to be significant, the interaction term will be omitted and an overall treatment effect will be tested.

D. QUALITY ASSURANCE

D1. Procedures in place to ensure the validity and integrity of the data

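### Abstinence from other substances is a named secondary outcome, but its only SAP measure counts opioids as well, so it cannot isolate non-opioid use

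*SAP*

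**What the plan says.** The list of secondary outcomes in the SAP's opening trial description includes "abstinence from other substances, time to relapse or dropout, and adverse effects". The protocol uses the same wording in its Lay Summary and in Specific Aims and Hypotheses.

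SAP A2, Secondary Outcomes, item 4, turns this into weekly yes/no measures that combine urine and self-report. One is opioid-specific, "reflecting whether each patient had urine-confirmed opiate-free weeks over the course of treatment". The other is "urine-confirmed abstinence from all drugs (dichotomous, longitudinal". SAP C3 says how they are analysed: "Longitudinal dichotomous and continuous outcomes will be modeled with generalized linear mixed effects models using appropriate link function".

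Both urine panels contain opioids. The SAP collects "urine toxicology for opioids (morphine, oxycodone, buprenorphine, methadone, propoxyphene, and fentanyl), THC, cocaine, benzodiazepines, amphetamines, and metamphetamines". The protocol (Assessment Instruments, Urine Toxicology) states that "the sample will be analyzed for substances of abuse, including THC, alcohol, opioids, cocaine, benzodiazepines, amphetamines, and barbiturates".

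Non-opioid use is named on its own in A2 only among the covariates and predictors: "Other substance use during treatment period".

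On self-report, the protocol's Timeline Follow-Back (TLFB) paragraph says that the interview gathers "opioid use data for each day during the month prior to study enrollment and each day during the study period". The same paragraph also calls the urine-confirmed TLFB the main measure of psychoactive substance use generally.

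**The concern.** The named outcome and its measure differ. A week with an opioid-positive urine fails the all-drug measure whatever the other results show, so that measure is a composite of opioid and non-opioid abstinence. Two things follow.

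- If XR-NTX reduces opioid use and leaves other drug use unchanged, the all-drug measure will still tend to favour XR-NTX.
- If participants in one arm move to other drugs, fewer opioid-positive weeks in that arm can offset the rise.

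Substitution is a natural question when an opioid is withdrawn. Under the listed outcomes, a reader who wants to know about it would have only a measure in which the opioid effect is mixed in.

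**Working it through.** **Inputs.** From SAP A4: 25 per arm, two-sided 5%, and example success of 40% (taper) and 77% (XR-NTX). Not in the documents, so assumed: the probability q of abstinence from non-opioid drugs, set equal in both arms so that the true non-opioid odds ratio (OR) is 1.

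**The plan's own figure.** SAP A4 states 80% power for 40% vs 77%. With unpooled variance, SE = √(0.40×0.60/25 + 0.77×0.23/25) = 0.129. Then 0.37/0.129 − 1.96 ≈ 0.90, and power is 81.7%. The pooled formula gives 77.3%. The stated figure is reproduced closely enough, and its two rates are used below.

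**Carry-over if opioid and other drug use are independent.** All-drug abstinence is 0.40q (taper) and 0.77q (XR-NTX). Power is from the pooled two-proportion formula.

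| q | Taper | XR-NTX | Difference (points) | OR | Power |
|---|---|---|---|---|---|
| 0.9 | 36.0% | 69.3% | 33.3 | 4.01 | 66% |
| 0.8 | 32.0% | 61.6% | 29.6 | 3.41 | 56% |
| 0.7 | 28.0% | 53.9% | 25.9 | 3.01 | 46% |
| 0.5 | 20.0% | 38.5% | 18.5 | 2.50 | 30% |
| 0.3 | 12.0% | 23.1% | 11.1 | 2.20 | 17% |

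A measure limited to non-opioid drugs would compare q with q: difference 0, OR 1.

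**Carry-over if the two kinds of use overlap fully.** All-drug abstinence is then min(p, q), where p is the arm's opioid abstinence.

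- q ≥ 0.77: 40% vs 77%, 37 points, OR 5.02
- q = 0.7: 40% vs 70%, 30 points, OR (0.70/0.30)/(0.40/0.60) = 3.50
- q = 0.6: 40% vs 60%, 20 points, OR (0.60/0.40)/(0.40/0.60) = 2.25
- q = 0.5: 40% vs 50%, 10 points, OR (0.50/0.50)/(0.40/0.60) = 1.50
- q ≤ 0.40: no difference, OR 1

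Full overlap therefore gives a smaller difference than independence when other drug use is common and a larger one when it is uncommon. The two are equal where q − 0.40 = 0.37q, that is q = 0.40/0.63 ≈ 0.63.

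**Masking, under independence.** Suppose non-opioid abstinence is 80% on taper and 60% on XR-NTX, so that other drug use doubles from 20% to 40%. All-drug abstinence is 0.40×0.80 = 32% against 0.77×0.60 = 46.2%. The OR is (0.462/0.538)/(0.32/0.68) = 1.82 in favour of XR-NTX. The composite stops favouring XR-NTX only when its non-opioid abstinence falls to 0.32/0.77 ≈ 42%.

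**How often a significant opioid result carries over.** In simulated trials with 25 per arm, independence and the pooled test, a significant opioid result came with a significant all-drug result in 37% of trials at q = 0.5, 60% at 0.7, 73% at 0.8 and 85% at 0.9. Carry-over is real but partial.

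**The case against.** The strongest reply is that all-drug abstinence is a legitimate measure, correctly named in A2 and placed in the same item as opiate-free weeks. Nothing in C3 says that it will be read as non-opioid use. That is fair, and the composite need not be dropped. But two marginal rates do not give non-opioid use unless their overlap is known, and the outcome that the plan names still has no measure of its own.

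Four stronger readings are tempting, and the documents do not support them.

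- *The substitution question cannot be answered.* It can. Non-opioid urine results are collected at study visits, and A2 already lists other substance use as a variable. What is missing is a prespecified outcome.
- *A positive opioid result automatically makes the all-drug result positive.* It does not, as the simulation shows.
- *The TLFB records opioids only.* One sentence points that way and the next points to all psychoactive substances. The text is ambiguous.
- *The odds ratios forecast this trial.* They do not. The rates of 40% and 77% are person-level week-25 figures from an example of a detectable difference. Item 4 is a repeated weekly outcome in a mixed model, and the documents give no weekly opioid-free rate.

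A non-opioid measure also has its own weakness. Benzodiazepines are on both panels, and the study supplies clonazepam: during Regimen 1 induction in both documents, and as an offer in Regimen 2 in the protocol only. Without a scoring rule the new measure could carry a treatment artefact. This objection stands, and the fix has to deal with it.

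**Conclusion.** The point holds as a mismatch between a named secondary outcome and its only measure. Followed as written, the plan yields a composite that carries part of the opioid effect and can hide a change in non-opioid use.

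The illustrative size is an odds ratio of 2.2 to 4.0 under independence with q from 0.3 to 0.9, and anywhere from 1.0 to 5.0 under full overlap over the same range, where the non-opioid odds ratio is 1. This rests on the SAP's example rates, an assumed q equal in both arms, and a single time point standing in for a weekly series. It also takes the plain meaning of all drugs; if the sponsor meant non-opioid drugs only, the wording needs the same correction.

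This is one component of one secondary outcome in a trial that calls itself exploratory. The primary outcome, both study aims and the sample size are untouched. The change is worth making because it is cheap, and because a non-opioid outcome defined only after the data are seen in an open-label trial would be a post hoc choice.

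**What to change.** 1. In SAP A2 item 4 and in C3, add a weekly outcome: free of non-opioid drugs, scored from the non-opioid urine results whatever the opioid result. Analyse it with the mixed model already planned for weekly dichotomous outcomes.
2. Report it beside opioid-free weeks and all-drug abstinence, with the last labelled as a composite that includes opioids.
3. List the drugs that count. The two panels differ: the protocol adds alcohol and barbiturates, and the SAP names methamphetamines separately.
4. State how benzodiazepine positives are scored in weeks when the study supplies clonazepam, for example by leaving benzodiazepines out of the measure in those weeks in both arms. The protocol and the SAP should first be reconciled on whether Regimen 2 includes these adjuvant medications.
5. State how buprenorphine positives during the taper count in the all-drug composite.
6. In the protocol's TLFB paragraph, state whether non-opioid days are recorded. If they are not, the new outcome is urine-only and should say so.

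Cost: a few lines in the SAP, one sentence in the protocol and one derived variable. No new visit, sample or assay is needed.

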monthly for therapy and monitoring. The primary outcome will be a binary indicator of discontinuation success, the percent of patients successfully transitioned off BUP and abstinent from opioids at the end of the trial, 25 weeks after randomization. We hypothesize that success rate will be greater in patients that received treatment with XR-NTX.

Setting and Screening: This study will be conducted at the BSU clinic at NYSPI where we have previously carried out recruitment and treatment of opioid-dependent subjects using similar methodology. A combination of radio, print, and Internet advertising will be directed at prospective participants in the New York metropolitan area. Screening procedures are standardized for clinical trials including a telephone interview, the MINI International Neuropsychiatric Interview, psychiatric evaluation, medical history, physical and laboratory examination. The research psychiatrist will offer eligible individuals participation in the study and will obtain informed consent.

Randomization. We predict that 50 participants (out of 60 enrolled) will complete lead-in phase successfully and will be available for randomization. The 1:1 randomization will be stratified by the BUP maintenance dose (4 mg/d vs. greater than 4 mg/d) and the type of the primary drug (prescription opioids vs. heroin) distributing these potential prognostic factors equally between groups to ensure comparable representation. The randomization sequence will be carried out by a research pharmacist, balanced in random blocks to protect allocation concealment.

Regimen 1 will include a rapid Monday to Friday oral naltrexone-induction procedure: last dose of BUP on Sat, Sun-Mon 0 mg, Tue 1 mg, Wed 3 mg, Thu 6 mg dose of oral NTX respectively. On Friday, a final 25 mg dose of oral NTX will be given followed by an injection of XR-NTX (Vivitrol; 380 mg IM). All doses of oral NTX will be given in a single or split doses depending on patients' tolerability of the protocol. Throughout the induction adjuvant medications will be administered on standing basis: clonidine 0.1 mg qid, clonazepam 0.5 mg qid, and zolpidem 10 mg HS. Additional injections of XR-NTX will be administered 4 and 8 weeks after the first injections to participants who provide an opioid-negative urine or pass a naloxone challenge test.

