The primary purpose of this proposed R21 is to estimate the 95% confidence interval (CI) for the treatment effect size, in this case the odds ratios of treatment success. The resulting 95% CIs provide considerably more information than hypothesis tests; it provides a range of plausible parameter estimates. Such range of effect sizes (especially the estimates from the lower end of the 95% CIs) can be used to conservatively estimate potential effect size in larger clinical trials. The following power calculations are only in support of this study proposal and for the purpose of sample size calculation. We assume that the observed proportion of successful BUP discontinuation in the buprenorphine taper group ranges from 30-50% (we assume higher success rate than in the previous buprenorphine taper studies due to longer period of stabilization). With 25 subjects in each arm, we have 80% power to detect a significant treatment success difference of 37% (e.g. 40% of treatment success in BUP compared to 77% treatment success in XR-NTX arm) on 5% level of significance. This is a robust effect that would be clinically meaningful.

The primary aim of this pilot study is to evaluate feasibility, tolerability, acceptability, and safety of two methods of discontinuing treatment with buprenorphine. The proposed sample size of 60 enrolled and 50 individuals randomized to two treatment arms can provide useful information for subsequent confirmatory clinical trial. We have chosen this sample size to minimize the cost and also to reach the study end within two years. 50 randomized subjects will provide large enough sample size to estimate the potential effect size in 95% confidence interval with reasonable precision.

B. TRIAL MANAGEMENT

B1. Data Collection Centers

All data will be collected at one site: New York State Psychiatric Institute's Outpatient Substance Abuse Research Service (STARS)-downtown at [name]. In our center, we have adopted StudyTrax, a comprehensive electronic system for clinical trials, which we will use to collect and manage data. As many entry forms and study calendars are already programmed, starting of a study can be expedited. Data will be analyzed using SPSS-PC, SAS, and HLM.

B2. Projected Time Table

Based on the recent rate of recruitment in our center and the planned sample size the study is estimated to take 24 months to complete.

B3. Target Population Distribution

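### The longitudinal and time-to-relapse analyses do not clearly adjust for the two factors used to stratify randomisation, and the dose stratum is not tied to the dose covariate in the SAP

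*SAP*

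**What the plan says.** Protocol, Study Procedures, Randomization: "The 1:1 randomization will be stratified by the BUP maintenance dose", with one level for 4 mg/d and the other for anything above it, and also by primary drug (prescription opioids or heroin). The reason given is that both may be prognostic.

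The SAP does not mention this stratification. Section C3 treats the analyses as follows.

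- **General statement** (significance testing and preliminary analysis): the analysis is adjusted for primary opioid type, length of buprenorphine maintenance and average dose.
- **Primary outcome:** "logistic regression adjusted for specified covariates (primary opioid type, length of BUP maintenance, and average dose").
- **Other dichotomous outcomes:** logistic regression on the same lines as the primary, so the three covariates carry over.
- **Longitudinal outcomes:** mixed models "with treatment, time, treatment by time interaction, and applicable baseline outcome measure as predictors".
- **Time to relapse:** survival methods and Kaplan-Meier estimation, with no covariate, stratification or test named.

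The dose covariate appears in section A2 as "Length of BUP treatment prior to randomization and the average dose". No averaging period or coding is given.

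**The concern.** Stratified randomisation balances the arms on the strata. If the strata predict outcome, the treatment estimate varies less between hypothetical repeats of the trial. A linear model that omits the strata leaves their variance in the residual and does not credit that balance. Its standard error is then too large, its test conservative and its interval too wide.

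This matters here for two reasons. Study Aim #2, on severity of protracted withdrawal, rests on a longitudinal model of the kind that lists neither factor. And SAP section A4 describes the trial as chiefly an exercise in interval estimation, with about 50 randomised participants.

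There is also a specification problem. One sentence in C3 suggests three covariates throughout, and the next section gives a different list for the longitudinal models. Two analysts could follow the same SAP and fit different models.

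**Working it through.** **1. The plan's own figure.** Section A4 states: "With 25 subjects in each arm, we have 80% power to detect a significant treatment success difference of 37" percentage points, for example "40% of treatment success in BUP compared to 77% treatment success in XR-NTX arm". The unpooled normal approximation at two-sided 5% gives:

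- variance term = 0.40 × 0.60 + 0.77 × 0.23 = 0.4171
- SE = √(0.4171/25) = 0.1292
- power = Φ(0.37/0.1292 − 1.96) = Φ(0.90) = 81.7%

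This reproduces the stated 80% within 2 points. The calculation is unadjusted and does not involve the strata, so it does not bear on this point.

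**2. Continuous outcome, without a baseline score.** Let R² be the share of outcome variance that the two factors explain. The documents do not give it, so 0–30% is an assumed range. Omitting the factors overstates the SE by 1/√(1 − R²) − 1. The unadjusted SE in SD units is about √(2/25) = 0.283. Simulation: 4,000 trials per setting, 50 participants, blocks of 4 within four strata, a 0.8 SD effect and a single time point.

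| R² | SE excess | SE omitted → included | Power omitted → included |
|---|---|---|---|
| 0% | 0% | no change | 79.3% → 78.9% |
| 5% | 2.6% | 0.282 → 0.274 | 80.3% → 81.5% |
| 10% | 5.4% | 0.282 → 0.268 | 79.9% → 82.8% |
| 20% | 11.8% | 0.282 → 0.252 | 81.7% → 87.4% |
| 30% | 19.5% | 0.282 → 0.236 | 82.4% → 90.8% |

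With the strata omitted, type I error was 3.8% at R² = 10% and 2.3% at 30%, against about 5% when they were included. The Monte Carlo SE of each power figure is about √(0.8 × 0.2/4000) = 0.6 point.

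**3. Allowing for the baseline score.** The planned longitudinal models adjust for baseline. Assume a within-stratum baseline–outcome correlation of 0.6, so the residual variance with strata and baseline in the model is 0.64(1 − R²).

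- If the strata shift baseline and outcome equally, the residual variance with baseline alone is 1 − [R² + 0.6(1 − R²)]². At R² = 10% the SE excess is √(0.5904/0.576) − 1 = 1.2%. At 20% and 30% it is 2.5% and 3.7%.
- If the strata do not act on baseline, the residual variance with baseline alone is R² + 0.64(1 − R²). The SE excess is √(0.676/0.576) − 1 = 8.3% at R² = 10%, then 17.9% and 29.2%.

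The figures in step 2 lie between these cases.

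**4. Logit outcomes.** Simulation: 2,500 trials per setting, one time point, marginal success 40% vs 77%, each factor given the odds ratio shown (assumed).

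| OR per factor | Log-OR omitted → included | SE omitted → included | Power omitted → included |
|---|---|---|---|
| 1 | 1.70 → 1.75 | 0.64 → 0.66 | 77.5% → 79.2% |
| 2 | 1.70 → 1.86 | 0.64 → 0.69 | 76.1% → 78.8% |
| 4 | 1.70 → 2.14 | 0.64 → 0.77 | 79.1% → 85.2% |

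Here omission makes the SE smaller. Power falls because the estimate is pulled towards zero. The rise at OR 1, where the strata carry no information, suggests that 1 to 2 points of each gain is small-sample behaviour of the logistic model.

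**5. Average dose or dose stratum in the primary model.** Power for average dose → two-level stratum, in three simulations with different assumptions:

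- Effect acts through the category, dose known exactly: 78.9% → 79.2%, 78.4% → 78.8% and 84.7% → 85.2% at OR 1, 2 and 4.
- Average dose taken as dose plus noise: 79.1% → 79.5%, 83.7% → 84.0% and 85.5% → 87.1% for weak, moderate and strong prognosis.
- Effect linear in mg: 81.5% → 80.4% (moderate) and 87.5% → 81.1% (strong).

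The change ranges from +1.6 to −6.4 points, so its sign depends on the assumption.

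**6. Coding of the stratum.** Eligibility covers 2–8 mg/d. The strata are described as 4 mg/d and above 4 mg/d, so a participant on 2 mg/d falls in neither as written.

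**The case against.** The strongest reply is that the general sentence in C3 comes before both the primary and secondary sections and already covers every model. It also names opioid type, which is one stratification factor, and average dose, which is close to the other. Participants stay on their usual dose during the one-month lead-in, so an average over that period would be nearly the dose that defined the stratum. This reading is possible. It is not secure, because the longitudinal sentence then gives its own list, and it never names the randomised dose category.

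Much of the rest of the reply stands. A reader might infer that the stratification factors are ignored in every planned model, or in all the secondary ones. The documents do not support that: the primary model and the dichotomous models that follow it adjust for opioid type and average dose. Nothing defines average dose as a treatment-history average that departs from the maintenance dose; its window is simply unstated. A reader might also infer that standard errors are too large throughout. That is wrong for logit models (step 4), and odds ratios are the stated estimation target. Finally, the error is in the conservative direction, mostly affects secondary outcomes of an exploratory trial, and could be nil, since the protocol calls the strata only potentially prognostic.

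**Conclusion.** The concern holds for the longitudinal mixed models and the time-to-relapse analysis, where the SAP does not clearly adjust for the factors used to randomise. For continuous outcomes the SE excess is about 5%, 12% and 20%, and the power loss about 3, 6 and 8 points, at R² of 10%, 20% and 30%. For logit outcomes there is attenuation and a loss of about 3 points (OR 2) to 6 points (OR 4), part of it a small-sample effect.

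These sizes rest on assumed prognostic strength, an assumed dose mix and a single time point standing in for the mixed model. With no prognostic strength there is no loss. With a baseline score that carries the strata's effect, the SE excess is about 1–4%.

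It might seem to follow that the primary model should swap average dose for the two-level stratum. Step 5 does not support that. What the primary model needs is a definition of average dose.

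**What to change.** In SAP section C3, Secondary Analyses:

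1. Add primary opioid type and the randomisation dose stratum as fixed effects in the longitudinal mixed models, both continuous and dichotomous.
2. For time to relapse, name a log-rank test or Cox model that is stratified by, or adjusted for, both factors.
3. State which analyses the general three-covariate sentence covers.

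Keep average dose in the primary logistic model and the dichotomous models that follow it. Define its averaging period and coding, and say how it relates to the dose used for stratification.

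Reconcile the stratum description in the protocol with the 2–8 mg/d eligibility range, and record the coding actually used at randomisation for participants on 2 mg/d.

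The cost is SAP wording and about 2 degrees of freedom in the affected models. Both factors should be on record from randomisation, so no new data are needed.
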